4.1 Procedures by Study Day

The following procedures will be performed during the study. Timings for sample collections and procedures are provided in [Appendix 12.1](#).

4.1.1 Screening Period (Day –28 to –1)

The following procedures will be performed within 28 days prior to the Day 1 visit of Cycle 1, unless otherwise specified:

- A signed and dated Institutional Review Board (IRB) /Independent Ethics Committee (IEC) approved informed consent form (ICF) obtained prior to performing any study evaluations. Results (e.g., from laboratory tests or radiographic evaluations, etc.) obtained prior to the date of informed consent but within the allowed timeframe for screening may be used for determination of patient eligibility only if obtained as part of the patient's standard of care.
- Demographic characteristics.
- Medical history (to include a complete history of all surgeries and significant diagnoses and all cancer treatment [including surgery, radiation therapy, chemotherapy, etc.]).
- Blood or urine β -HCG pregnancy testing (women of childbearing potential only).
- Physical examination including whole body skin assessment. The whole body skin assessment does not have to be performed by a dermatologist. However, any unexplained lesion is to be referred to a dermatologist for further evaluation and skin biopsy, if clinically warranted.
- Vital signs (arterial blood pressure, heart rate, respiratory rate, body temperature), height and weight measurements.
- ECOG performance status.

- Disease assessment: Positron emission tomography - computed tomography (PET-CT) and diagnostic CT of the neck/chest/abdomen/pelvis and other areas of known disease or newly suspected disease with a clinical examination for lymphoma. Contrast should be used unless contraindicated. Magnetic resonance imaging (MRI) is permitted if diagnostic CT is contraindicated. The same assessments methods used at Screening which identify sites of disease should be used uniformly for all subsequent assessments.

Note: PET-CT is only required at screening for 18F-fluorodeoxyglucose (FDG) avid, nodal

lymphomas (defined as per the Lugano Classification criteria as essentially all eligible histologies except small lymphocytic lymphoma, lymphoplasmacytic lymphoma/Waldenstrom's macroglobulinemia, mycosis fungoides, and marginal zone NHLs, unless there is a suspicion of aggressive transformation). If PET-CT examination is negative at Screening, subsequent PET-CT is not required. If PET-CT is positive, subsequent diagnostic CT and MRI are not needed unless clinically indicated.

- Hematology, coagulation panel, biochemistry, and urinalysis parameters.
- 12-lead electrocardiogram (ECG).
- Collection of adverse event (AE) information.
- Collection of information on medications used (including prescription or over-the-counter medication, herbal or naturopathic products) within the 14 days prior to the Day 1 visit.

4.1.2 Day 1 of Each Cycle

The following procedures will be performed prior to ADCT-402 infusion (unless otherwise indicated) at each cycle, unless otherwise specified.

- Blood or urine β -HCG pregnancy test required if the pregnancy test was obtained >7 days prior to Day 1 (every other cycle).
- Physical examination including whole body skin assessment, unless an assessment was performed within 3 days prior to Day 1.
- Vital signs: On Day 1 of Cycles 1 and 2, vital signs are to be measured before the start of the ADCT-402 infusion, every 30 minutes during the infusion, at the end of infusion, and at 1, 3, and 6 hours after the end of infusion. If no clinically significant changes occur during Cycles 1 and 2, vital sign measurements are to be obtained prior to infusion start and end of infusion for all subsequent infusions. If clinically significant changes in vital signs are observed at Cycle 1 and/or 2 infusion, that patient will be required to have vital signs measured before the start of the ADCT-402 infusion, every 30 minutes during the infusion, at the end of infusion, and at 1, 3, and 6 hours after the end of the ADCT-402 infusion for all subsequent cycles.
- Weight.
- ECOG performance status.
- Samples for hematology, coagulation panel, biochemistry parameters, will be measured prior to dosing unless the last sample was collected:
 - <24 hours before the start of ADCT-402 infusion on Day 1 of Cycle 1, or
 - <72 hours before the start of ADCT-402 infusion on Day 1 of Cycle 2 and subsequent cycles.

- Sample collection for additional renal function studies.
- Sample collection for urinalysis

Prior to dosing unless the last sample was collected:

- <24 hours before the start of ADCT-402 infusion on Day 1 of Cycle 1, or
- <72 hours before the start of ADCT-402 infusion on Day 1 of Cycle 2 and subsequent cycles.

- Disease assessment:

Patients Initially Treated Every 3 weeks

- To be conducted within 6 days prior to Day 1 of Cycles 3 and 5 and thereafter every third cycle (i.e., Cycles 8, 11, 14, etc.), until disease progression, or more frequently, if clinically indicated.
- Patients who initially follow a three-week dose schedule and then transition to a six-week schedule following Cycle 2 should have disease assessments ~6 weeks after Cycle 1 Day 1, and ~12 weeks after Cycle 1 Day 1, and thereafter at least every 12 weeks.

Patients Initially Treated Every 6 weeks

[figure not shown]
- For patients who have reduced dosing frequency and are following a 6 week schedule, disease assessments should occur approximately 6 weeks and 12 weeks after Cycle 1 Day 1, and thereafter at least every 12 weeks. It is understood that there will be a ± 6 day window for restaging of these patients.
- For patients in Part 2: Treatment continuation will require independent verification of the local response assessment unless otherwise approved by the sponsor.

In case of dose delays, please refer to [Section 6.1](#) for the frequency of disease assessments.

The same methods used at Screening which identify sites of disease should be used uniformly for all subsequent assessments. If PET-CT is positive, subsequent diagnostic CT and MRI are not needed unless clinically indicated.

If PET-CT examination is negative at Screening, subsequent PET-CT is not required.

- 12-lead ECG (Cycles 1 and 2) before the start of the ADCT-402 infusion, within 30 minutes of the end of infusion, and at 3 hours (± 30 minutes) and 24 (± 2.4) hours after the end of infusion. For Cycle 3 and subsequent cycles, a 12-lead ECG is to be performed before the start of ADCT-402 infusion.
- Sample collection for central laboratory analysis of ADA (all cycles).
- Sample collection (Cycles 1 and 2) for central laboratory analysis of PK parameters before the start of the ADCT-402 infusion, at the end of the infusion, and at 1, 3, and 6 hours after the end of the ADCT-402 infusion. For Cycle 3 and subsequent cycles, samples will be collected before the start of the ADCT-402 infusion and at the end of the infusion.

- 
- Collection of AE information.
 - Collection of concomitant medication information.
 - Premedication administration, if applicable ([Section 5.2](#)).
 - ADCT-402 administration.

4.1.3 Day 2 (Cycles 1 and 2)

The following procedures will be performed 24 hours ($\pm 10\%$) after the end of the ADCT-402 infusion:

- 12-lead ECG.
- Vital signs
- Sample collection for central laboratory analysis of PK parameters.
- Collection of AE information.
- Collection of concomitant medication information.

4.1.4 Day 3 (Cycles 1 and 2)

The following procedures will be performed 48 hours ($\pm 10\%$) after the end of the ADCT-402 infusion:

- Vital signs.
- Sample collection for central laboratory analysis of PK parameters.
- Collection of AE information.
- Collection of concomitant medication information.

4.1.5 Day 5 (Cycles 1 and 2)

The following procedures will be performed 96 hours (± 1 day) after the end of the ADCT-402 infusion:

- Sample collection for central laboratory analysis of PK parameters.
- Vital signs.
- Collection of AE information.
- Collection of concomitant medication information.

4.1.6 Day 8 (± 2 days) of Each Cycle

- Physical examination (Cycles 1 and 2) including whole body skin assessment.

- Weight
- Vital signs.
- Hematology and biochemistry parameters.
- Urinalysis and sample collection for additional renal function studies.
- Sample collection for central laboratory analysis of PK parameters (Cycles 1-4).
- Collection of AE information.
- Collection of concomitant medication information.

4.1.7 Day 15 (\pm 2 days) of Cycles 1 and 2

The Day 15 visit will be conducted during Cycles 1 and 2 only; the following procedures will be performed at this visit:

- Physical examination including whole body skin assessment.
- Weight.
- Vital signs.
- Hematology and biochemistry parameters.
- Urinalysis and sample collection for additional renal function studies.
- Sample collection for central laboratory analysis of PK parameters.
- Collection of AE information.
- Collection of concomitant medication information.

4.1.8 Day 28 (\pm 3 days)

For patients who have transitioned to a reduced dosing frequency (see [Section 3.1](#)) this visit will be required for Safety/PK Monitoring. Assessments required for Safety/PK Monitoring are indicated below. For patients in Part 1 this visit will be done approximately 21 days after infusion.

- Physical examination
- Vital signs
- Weight
- ECOG
- 12-lead ECG
- Sample collection for hematology, coagulation panel, and biochemistry parameters
- Sample collection for urinalysis

- Sample collection for additional renal function studies.
- Sample collection for central laboratory analysis of PK parameters and ADA.
- Collection of AE information
- Collection of concomitant medication information

4.1.9 End of Treatment Visit

The following procedures will be performed within 30 days after study treatment discontinuation and prior to initiation of new anticancer treatment:

- Physical examination including whole body skin assessment.
- Weight and vital signs.
- ECOG performance status.
- Disease assessments:
 - Patients who already have documented objective disease progression do not need to have assessments repeated.
 - Patients who do not already have documented objective disease progression will have assessments performed at the end of treatment visit if the most recent disease assessment was >9 weeks prior to the end of treatment visit.
- Blood or urine pregnancy test
- Hematology, coagulation panel, and biochemistry parameters.
- Urinalysis and sample collection for additional renal function studies.
- 12-lead ECG.
- Sample collection for central laboratory analysis of PK parameters and ADA.

- 
- Collection of AE information
 - Collection of concomitant medication information.

When EOT coincides with a scheduled visit, the scheduled visit will become EOT.

4.1.10 12-week Follow-up Visit

Each patient will have a blood sample taken for assessment of PK and ADA at 12 (\pm 1) weeks after their last dose of ADCT-402, unless a new anticancer treatment has been initiated.

Blood Sample Collection and Adverse Event Monitoring During Long-Term Follow-up

Patients who test positive for ADAs may be requested to supply additional ADA samples.

For all patients, collection of AEs and SAEs will continue for 12 weeks after the last dose of study drug or initiation of new anticancer treatment (see [Section 6.3.2.2](#)).

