4.1.11 Long-term Follow-up

Patients who discontinue treatment for any reason other than objective disease progression will continue to be followed with scans approximately every 12 weeks from the last tumor assessment until disease progression, or initiation of new anticancer treatment. If a patient discontinues treatment for a hematopoietic stem cell transplant, the frequency of imaging will be as per the transplant center standard of care.

After documentation of disease progression or start of new treatment, patients will be contacted by telephone approximately every 12 weeks for up to 12 months after the last dose of study drug to collect survival information.

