- 18 12-lead ECG to be performed on Day 1 of Cycles 1 and 2, a 12-lead ECG is to be performed before the start of the ADCT 402 infusion, within 30 minutes of the end of infusion, and 3 (\pm 30 minutes) and 24 (\pm 2.4) hours after the end of infusion.
- 19 See [Section 12.1.2](#) of this Appendix for sample timing.
- 20 [REDACTED]
- 21 Concomitant medications to include prescription or over-the-counter medication, herbal or naturopathic products within the 14 days prior to the Cycle 1, Day 1 visit and during the study.
- 22 Premedication to be performed if grade 2 or higher infusion-related hypersensitivity reactions are observed in 1 patient at any time during Part 1 of the study, all subsequent patients must receive prophylactic treatment on Day 1 of each cycle thereafter to reduce the risk of hypersensitivity reaction.
- 23 ADCT-402: Patients will receive a 1-hour IV infusion at escalating doses, on Day 1 of each 3-week (21-day) cycle. If ADCT-402 is well tolerated after the first cycle, the infusion duration may be shortened to 30 minutes for subsequent cycles for that patient, at the Investigator's discretion. Variations in infusion times due to minor differences in IV bag overfill/under fill and the institution's procedure for flushing chemotherapy lines will not result in protocol deviation.
- 24 For all patients, collection of AEs and SAEs will continue for 12 weeks after the last dose of study drug or initiation of new anticancer treatment. Any SAEs that occur more than 84 days after the last dose of study drug do not need to be reported unless the Investigator considers the event to be related to study drug.
- 25 End of Treatment to occur within 30 days after last dose of ADCT-402 and prior to the initiation of new anticancer treatment. When EOT coincides with a scheduled visit, the scheduled visit will become EOT.
- 26 Follow-up to occur 12 (\pm 1) weeks after last dose of ADCT-402.
- 27 After completion of 6 treatment cycles (e.g., 6 infusions), the Day 8 visit is not required unless clinically indicated.
- 28 PK sample collection on Day 8 Cycles 1-4. Refer to [Section 6.1](#), Efficacy Assessments.
- 29 Sample for assessment of PK and ADA to be obtained 12 weeks (\pm 1 week) after last dose of ADCT-402, unless a new anticancer treatment has been initiated.

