#### **4.1.3 Efficacy Analysis Set**

The efficacy analysis set consists of patients who receive at least one dose of ADCT-402 with a valid baseline and at least one valid post-baseline disease assessment or patients who have documented progression of disease or death at any time after the first dose of study drug and before the start of any subsequent anticancer therapy or procedure.

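### A patient who stops early can leave with no post-baseline scan, because the end-of-treatment rule counts the baseline scan; the SAP then removes that patient from the ORR denominator and from OS

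*Protocol*

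**What the plan says.** Protocol 4.1.9 asks for no repeat assessment at EOT once progression is documented. For everyone else, one is due "if the most recent disease assessment was >9 weeks prior to the end of treatment visit". It does not say what applies when the only assessment on record is the baseline one.

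The timings that matter are:

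- **Baseline.** Imaging is part of screening: "The following procedures will be performed within 28 days prior to the Day 1 visit of Cycle 1" (Protocol 4.1.1).
- **First on-study assessment (Protocol 4.1.2).** For the 3-week schedule: "To be conducted within 6 days prior to Day 1 of Cycles 3 and 5". For the 6-week schedule: "disease assessments should occur approximately 6 weeks and 12 weeks after Cycle 1 Day 1".
- **EOT visit.** Protocol 4.1.9 allows 30 days from treatment discontinuation. The schedule footnote in 12.1.1 counts from another date: "End of Treatment to occur within 30 days after last dose of ADCT-402".
- **After stopping for a reason other than progression.** Patients are "followed with scans approximately every 12 weeks from the last tumor assessment until disease progression, or initiation of new anticancer treatment" (Protocol 4.1.11).

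SAP 4.1.3 admits a treated patient "with a valid baseline and at least one valid post-baseline disease assessment". It also admits, without a scan, a patient with documented progression or death before subsequent anticancer therapy. SAP 4.9.2, 4.9.4 and 4.9.5 assign DOR, PFS and OS to this set. SAP 4.9.1 names no set for ORR, but SAP 3.3 presents the set as the definition of who is evaluable for efficacy, so it is the natural denominator. Protocol 7.4 had admitted patients with valid baseline data and two doses whether or not they were rescanned. The SAP no longer does.

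**The concern.** The 9-week limit is sensible for a patient with a recent on-study scan, because it avoids a redundant one. A baseline scan says nothing about response. For a patient who stops in the first weeks, the EOT visit is the last one the protocol places before new therapy, and it can pass without imaging. The next scan comes weeks later and is cancelled if new therapy starts. In relapsed or refractory lymphoma, a patient who stops for toxicity may well move on in that interval.

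What is at stake is the ORR denominator in Part 2 cohorts of about 10 to 20 (Protocol 7.3), where each patient counts. The SAP also treats like cases differently. Under 4.9.1 a patient whose only assessment is stable disease within 35 days of first dose becomes not evaluable, but stays in the denominator. A patient with no assessment at all is removed. For OS, the set makes membership depend on a scan that the endpoint does not need.

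**Working it through.** The plan states no figure for this point, so the check is calendar arithmetic followed by the effect on a proportion. There is no Day 0, so days elapsed = study day − baseline scan day − 1. Nine weeks is 63 days and 12 weeks is 84 days.

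**1. First scheduled post-baseline scan.** Cycle 3 Day 1 is Day 1 + 2 × 21 = Day 43. The 3-week schedule therefore gives Days 37 to 42. The 6-week schedule, with its ±6-day window, gives Days 37 to 49.

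**2. When the EOT rule and the follow-up rule require a scan, counted from baseline.**

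| Baseline scan | EOT scan due if EOT is on or after | 12-week follow-up scan |
|---|---|---|
| Day −28 | Day 37 | Day 57 |
| Day −14 | Day 51 | Day 71 |
| Day −1 | Day 64 | Day 84 |

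**3. One dose, EOT timed from last dose.** The latest EOT is Day 1 + 30 = Day 31. The baseline scan is then between 31 − (−1) − 1 = 31 and 31 − (−28) − 1 = 58 days old. This never exceeds 63, so no EOT scan is required. No distributional assumption is needed.

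**4. Two doses, 3-week schedule.** The latest EOT is Day 22 + 30 = Day 52, with the baseline scan 52 to 79 days old. Even then a scan is due only if 52 − s − 1 > 63, that is, if baseline imaging was on Day −13 or earlier.

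**5. Effect of the EOT timing conflict.** Suppose Cycle 2 (Day 22) is delayed by 21 days to Day 43 and treatment then stops. Under 4.1.9 the EOT could be as late as Day 73, with the baseline scan 73 to 100 days old, and a scan would be due. The *never* in step 3 therefore depends on the 12.1.1 footnote.

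**6. How often no EOT scan is due (assumption only).** Take baseline scans uniform over Days −28 to −1 and stops uniform over Days 2 to 36, which gives 28 × 35 = 980 combinations. No scan is due in 980/980 (100%) if EOT is on the stop day, 875/980 (89%) if 14 days later and 518/980 (53%) if 30 days later. With the lag uniform over 0 to 30 days the share is 84%. These are shares with no EOT scan due, not shares lost from the efficacy set.

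**7. Effect on ORR.** A patient with no post-baseline assessment cannot be a recorded responder. Removing k such patients changes x/n to x/(n − k), which cannot be lower. For x = 8 and n = 20, with exact 95% intervals:

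| Removed | ORR | 95% CI |
|---|---|---|
| 0 | 8/20 = 40.0% | 19.1 to 63.9 |
| 1 | 8/19 = 42.1% | 20.3 to 66.5 |
| 2 | 8/18 = 44.4% | 21.5 to 69.2 |
| 3 | 8/17 = 47.1% | 23.0 to 72.2 |

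The losses of 5%, 10% and 15% are assumed; the documents give no rate.

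**8. Effect on PFS.** SAP 4.9.4 censors patients with no post-baseline assessment on Day 1. Including or excluding them leaves the Kaplan-Meier curve essentially unchanged.

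**The case against.** The strongest reply is that the plan does not abandon these patients. Protocol 4.1.11 keeps them on 12-weekly scans, and one valid scan admits them to the set. Progression or death before new therapy admits them with no scan, and SAP 4.9 also accepts clinical progression from the EOT or disposition page. Protocol 4.1.9 does not forbid an EOT scan, and 4.1.2 and 6.1 allow extra assessments when clinically indicated. The table in 12.1.1 marks a disease assessment at EOT, with no footnote on that row limiting it. Some early toxicity will be managed by dose delay, during which 6.1 keeps assessments on schedule, so some of these patients reach the Week 6 scan. All of this stands. A reader might infer that every early toxicity stopper leaves unscanned and drops out of the set. The documents do not support that.

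A reader might also infer that the rule distorts dose selection. Protocol 6.3.1.1 has the steering committee set dose levels and the MTD from safety findings and DLTs. Part 2 dosing rests on safety, efficacy and PK together, and the safety set is all treated patients. The Part 1 rule of at least 3 responders among 10 counts treated patients (Protocol 3.2). No hypothesis is tested. More losses at more toxic doses are plausible but not shown.

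The objection does not remove the remaining case. A scan that is permitted is not a scan that is required, and the follow-up scan ends with new therapy. A patient who starts new therapy, withdraws or is lost before about Day 57 to 84, without documented progression or death, has been treated but is not counted.

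**Conclusion.** The point holds in this limited form. The EOT rule lets the baseline scan stand as the most recent assessment, so a patient who stops before Week 6 usually has no EOT scan due. After a single dose, with EOT within 30 days of last dose, none is ever due. If the follow-up scan is then lost, the SAP removes a treated patient who is not a recorded responder from the ORR denominator, and removes the same patient from OS.

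Relative to all treated patients with a valid baseline, the effect on ORR can only be upward. Its size is unknown. The 42% to 47% figures illustrate one to three losses in a cohort of 20; they are not an estimate, and they lie well within the sampling error of such a cohort. The direction of any effect on OS cannot be determined from the documents. A claim of bias in PFS is not supported. The exclusion comes from the SAP set definition at least as much as from the EOT rule, so the SAP is where the main correction belongs.

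**What to change.** 1. **SAP 4.1.3, 4.9.1 and 4.9.5 (main change).** State the ORR denominator as all treated patients with a valid baseline, and class those with no post-baseline assessment as not evaluable, counted as non-responders. At the least, report this beside the efficacy-set ORR. Analyse OS on all treated patients. Also align 3.3 with 4.1.3: only the latter limits progression or death to the period before subsequent therapy.
2. **Protocol 4.1.9 (secondary).** Extend the condition so that an EOT assessment is also due when no post-baseline assessment has been done, with that scan counting as the first follow-up scan. This does not solve everything: a lone stable-disease result within 35 days of first dose would still be not evaluable under SAP 4.9.1.
3. **Reconcile the EOT passages.** Section 4.1.9 limits the scan, while the EOT column in 12.1.1 marks it without that limit. Section 4.1.9 times the visit from discontinuation, and the 12.1.1 footnote times it from last dose.

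The cost is a few SAP sentences and one protocol clause. ORR becomes slightly less favourable. A few scans are done earlier, and because the 12-week clock then restarts at EOT, the next scan for those patients falls later than it otherwise might.
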